## 10. STAGE 2 PLANNED STATISTICAL METHODS

### 10.1 Determination of Sample Size

The chosen sample size of 72 subjects (i.e. 24 subjects per dose arm) is deemed sufficient to provide adequate precision to the estimation of the response rate in each treatment arm. The trial will enroll 84 subjects to allow for a discontinuation rate of 15%.

On the basis of the available data, it is assumed that the response rate on the primary endpoint will be 5% in the 0.3 mg/kg arm, 46% in the 10 mg/kg arm and at least 46% in the 3 mg/kg arm. A sample size of 24 subjects will ensure an absolute precision of +/- 8% to the evaluation of the response rate in the 0.3 mg/kg arm (assuming the response rate is 5%) and an absolute precision of +/- 20% of the response rate in the 3 mg/kg and 10 mg/kg arms (assuming the response rate is 46%).

In addition, with 24 subjects in each arm, the probability to demonstrate that the observed response rate in the 3 mg/kg and 10 mg/kg arms is larger than 10% by comparing the lower limit of the exact 97.5% two-sided confidence interval of the observed rate to 10% is larger than 0.999 (assuming the response rate is 46%)

In addition, it is planned to perform pairwise comparisons between dose arms as part of the secondary efficacy analysis. A sample size of 24 subjects per arm will ensure a power of 82% to detect a difference of 39% between two treatment arms (assuming the best response rate is 46%) with a two-sided type one error of 0.025. Consequently if the assumption of response rates of 5% in the 0.3 mg/kg arm and 46% in the 3 and 10 mg/kg arm is true, the study will be sufficiently powered (power = 82%) to demonstrate a significant superiority of any of the higher doses over the smallest dose, using an adjusted two-sided 0.025 type-one error rate.

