### 10.2. Randomization and Stratification

This study is randomized with a 1:1:1 randomization ratio. A central randomization system will be used. The randomization will be stratified according to the subject's baseline hematologic status: baseline anemia (Hgb < 100 g/L and having received  $\geq 2$  units PRBC in 12 weeks prior to study entry) alone or baseline thrombocytopenia (platelet count <  $50 \times 10^9/L$ ) alone; or baseline anemia associated with baseline thrombocytopenia. The randomization system will also ensure that at least 50% of the subjects in the final study population will have baseline thrombocytopenia.

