### **10.3.3. Inferential statistics**

The primary efficacy analysis is both descriptive and inferential. The exact confidence interval for the response rate in each arm will be computed and its lower bound will be compared to 10%.

In addition, one secondary objective of the study is to determine if there is a difference in efficacy between the three doses of PRM-151 used in the study. These comparisons will be done only if at least one dose arm is demonstrated to have a response rate superior to 10% in the primary analysis. The comparison between the 3 mg/kg arm and 10 mg/kg arm is not expected to be sufficiently powered to detect any statistically significant difference. The two main comparisons (3 mg/kg arm versus 0.3 mg/kg arm and 10 mg/kg arm versus 0.3 mg/kg) will use an adjusted type-one error rate of 0.025 to control the overall type-one error rate. The 3 mg/kg versus 10 mg/kg comparison will only be provided with an exploratory purpose and will be done without correction of the type-one error.

For all the other secondary efficacy analyses involving formal statistical comparisons, no adjustment of the type-one error rate will be conducted. As a consequence, the results of these tests will have to be interpreted bearing in mind the issue of multiplicity and the increased risk of erroneously obtaining statistically significant results.

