## 10.6. Planned Statistical Analyses and Methods

### 10.6.1 Efficacy Analyses

#### 10.6.1.1. Primary analysis of efficacy

The primary efficacy analysis will consist in computing the bone marrow response rate (percent of subjects with a reduction in bone marrow fibrosis score by at least one grade, see Section 3.1) and its 95% (unadjusted) and 97.5% (adjusted) two-sided confidence intervals within each treatment arm. This analysis will be conducted on the FAS analysis set.

Inferential interpretation: for the 3 mg/kg and 10 mg/kg arms, the lower limit of the 97.5% two-sided confidence interval will be compared to 10%, a threshold assumed to define the minimal clinically relevant effect. If the lower limit of the confidence interval is above 10%, the corresponding dose will be claimed to have demonstrated clinically relevant efficacy.

The confidence intervals computation will use a method consistent with the stratified design.

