### **10.6.1.3. Secondary and exploratory efficacy analyses:**

#### **10.6.1.3.1. Comparison of PRR between treatment arms**

Pairwise comparisons between the three dose groups will be performed using the Cochran-Mantel-Haenszel (general association) statistic in the SAS Freq procedure, to take into account the stratified design, using the following statement:

*tables Stratum\*Treatment\*Response / cmh;*

The Breslow-Day Test for Homogeneity of the Odds Ratios will be examined to detect a potential significant stratum difference in the odds ratios.

Two pairwise comparisons (3 mg/kg versus 0.3 mg/day and 10 mg/kg versus 0.3 mg/day) will be computed with the aim to demonstrating superiority and, consequently, will use an adjusted a two-sided 0.025 level of significance.

The third comparison (10 mg/kg versus 3 mg/kg) is not expected to have enough power to demonstrate any difference with the planned sample size. This comparison is considered exploratory and will be conducted using an unadjusted 0.05 level of significance.

These analyses will be computed on both the FAS (primary analysis set) and PP analysis sets.

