4.4 EFFICACY ANALYSIS

All analyses will be performed separately for each stage.

4.4.1 Primary Efficacy Endpoint

Stage 1:

The ORR will be compared against a fixed level of 10% using one-proportion Z-test.

The hypothesis test will be performed separately in each of the 4 treatment groups and overall, each at the 5% significance level (one-sided; statistical significance will be concluded if the lower bound of the 2-sided 90% CI is above 10%).

Subjects with no post-baseline IWG response assessments will be considered non-responders.

Stage 2:

The BMRR will be described as the percent of subjects with a reduction in bone marrow fibrosis score by at least one grade from baseline to any time of the study.

The BMRR will be presented within each treatment group with the corresponding 95% CI.

The BMRR will be analyzed using a logistic regression with bone marrow response at any time during the study (yes/no) as response variable and treatment group as explanatory variable. The analysis will be adjusted on randomized stratum. Pairwise comparisons between the 3 treatment groups will be performed.

Two pairwise comparisons (3 mg/kg versus 0.3 mg/day and 10 mg/kg versus 0.3 mg/day) will be computed with the aim to demonstrate superiority and therefore, will use an adjusted two-sided level of significance of 0.025. The third comparison (10 mg/kg versus 3 mg/kg) is not expected to have enough power to demonstrate any difference with the planned sample size. This comparison is considered exploratory and will be conducted using an unadjusted two-sided 0.05 level of significance.

The protocol proposed a threshold of 10% as the lower limit for clinically relevant response. For the 3 mg/kg and 10 mg/kg groups, the lower limit of the 97.5% two-sided confidence interval will be compared to this threshold of 10%. If the lower limit of the confidence interval is above 10%, the corresponding dose will be claimed to have demonstrated clinically relevant efficacy.

For subjects with no readable post-baseline BM biopsy results available, the conservative rule to consider them as non-responders will be used.

4.4.2 Secondary Efficacy Endpoints

Stage 1:

For Stage 1, no formal hypothesis testing will be performed for the secondary efficacy endpoints. All summaries will be presented by treatment group and overall.

The bone marrow biopsy results will be analyzed as:

- Myelofibrosis grade shifts relative to baseline at Weeks 12 and 24.

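### Holding both dose comparisons at a fixed 0.025 is valid, but Holm's step-down keeps the same 0.05 bound and raises the chance that both doses succeed from 85.1% to 91.4% at the planning rates

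*SAP*

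**What the plan says.** SAP 4.4.1 (Stage 2) makes three pairwise comparisons of bone marrow response rate. The two against 0.3 mg/kg aim at superiority, and each "will use an adjusted two-sided level of significance of 0.025". The comparison of 10 with 3 mg/kg is exploratory at an unadjusted 0.05. Protocol 10.6.1.3.1 has the same rule: "will use an adjusted a two-sided 0.025 level of significance". Protocol 10.3.3 gives its purpose: the two main comparisons "will use an adjusted type-one error rate of 0.025 to control the overall type-one error rate". That section also allows the comparisons only if at least one dose has first passed the 10% threshold. Neither document mentions a step-down procedure or any passing on of unused alpha.

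The 10%-threshold claims use the same split. In protocol 10.6.1.1, for the 3 and 10 mg/kg arms, "the lower limit of the 97.5% two-sided confidence interval will be compared to 10" percent. SAP 4.4.1 repeats this.

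Protocol 10.1 assumes response rates of "5% in the 0.3 mg/kg arm, 46% in the 10 mg/kg arm and at least 46% in the 3 mg/kg arm", with "72 subjects (i.e. 24 subjects per dose arm"). It states 82% power for a 39-point difference "with a two-sided type one error of 0.025". That is the power of one comparison; no probability is given that both doses succeed.

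**The concern.** Under the fixed rule, the second dose must still reach 0.025 after the first has been shown superior. Control of the familywise error does not require this. Once one of two null hypotheses has been rejected at 0.025, the other can be tested at 0.05 and the overall bound remains 0.05. This is Holm's procedure. It needs no assumption about the dependence between the two tests, which matters here because both share the 0.3 mg/kg arm.

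What is at stake is an answer on each dose. Finding out whether efficacy differs between doses is a secondary objective (protocol 2.2), and protocol 1.5 calls identifying the minimal effective dose important for further development. With about 24 per arm, one responder can decide whether the second dose is declared superior.

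**Working it through.** **Inputs.** Protocol 10.1: 24 evaluable per arm; rates 5% (0.3 mg/kg), 46% (10 mg/kg) and at least 46% (3 mg/kg, taken as 46%). Protocol 10.2: "This study is randomized with a 1:1:1 randomization ratio". The test is an uncorrected Pearson chi-square on each pair of arms, which agrees with the Cochran-Mantel-Haenszel test when strata are ignored. Ignoring strata is an assumption.

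**Step 1: reproduce the plan's 82%.** A 39-point difference from 46% means 46% against 7%. The mean rate is 0.265 and z for two-sided 0.025 is 2.241.
- Null standard error: √(2 × 0.265 × 0.735 / 24) = 0.1274.
- Alternative standard error: √((0.07 × 0.93 + 0.46 × 0.54) / 24) = 0.1143.
- Power: Φ((0.39 − 2.241 × 0.1274) / 0.1143) = Φ(0.914) = 82.0%.

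The stated 82% reproduces.

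**Step 2: where the two rules differ.** The critical chi-square values are 5.024 (0.025) and 3.841 (0.05). Suppose 1 of 24 respond on 0.3 mg/kg.
- 7 responders on a dose: 48 × (1 × 17 − 7 × 23)² / (24 × 24 × 8 × 40) = 5.40, significant at 0.025.
- 6 responders: 48 × (1 × 18 − 6 × 23)² / (24 × 24 × 7 × 41) = 4.18, significant at 0.05 only.

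If the other dose has 7 or more, Holm also accepts the dose with 6; the fixed rule does not.

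**Step 3: probability that both doses succeed.** Let b(x) be the binomial probability of x responders on 0.3 mg/kg. Given x, let a(x) and d(x) be the probabilities that one dose is significant at 0.025 and at 0.05. With equal dose rates, summing over x:
- Fixed rule, both: Σ b·a²
- Holm, both: Σ b·(2ad − a²)
- At least one, either rule: Σ b·(2a − a²)

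| Setting (0.3 / 3 / 10 mg/kg) | Fixed 0.025, both | Holm, both |
|---|---|---|
| 5% / 46% / 46%, 24 per arm | 85.1% | 91.4% |
| 7% / 46% / 46%, 24 per arm | 76.5% | 84.9% |
| 10% / 46% / 46%, 24 per arm | 62.4% | 72.9% |
| 5% / 35% / 46%, 24 per arm | 67.3% | 78.0% |
| 5% / 46% / 46%, 28 per arm | 90.7% | 94.7% |
| 5% / 46% / 46%, 24 per arm, Fisher | 75.6% | 84.5% |

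The fourth row has unequal dose rates and uses the corresponding product terms. In the first row Σ b·a = 0.9141, so at least one dose succeeds with probability 2 × 0.9141 − 0.8508 = 0.977 under either rule. Adding the protocol's 10% gate changes the first row to 85.05% and 91.34%.

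**Step 4: error when one dose is ineffective.** With 0.3 mg/kg and one dose both at 10%, the other dose at 46% and 24 per arm, the chance of a false claim for the ineffective dose is 1.7% (fixed) and 3.7% (Holm).

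**Step 5: the 10% claims, exact intervals.** At 24 per arm, 7 responders give lower limits of 11.0% (97.5% interval) and 12.6% (95% interval); 6 give 8.4% and 9.8%. The bar is 7 at either level, so Holm changes nothing: at 46% both doses pass with probability 0.9707² = 94.2%. At 28 treated the bar is 8 at 97.5% and 7 at 95%.
- Rate 46%: 0.9811² = 96.3% (fixed); 2 × 0.9811 × 0.9935 − 0.963 = 98.7% (Holm).
- Rate 39.1% (assumed, 0.46 × 0.85, dropouts counted as non-responders): 0.9116² = 83.1% (fixed); 2 × 0.9116 × 0.9612 − 0.831 = 92.1% (Holm).

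**The case against.** The main objection is timing, and it stands. The SAP's Background says that the earlier Stage 2 plan was signed before the Stage 2 primary database lock and analysis, and that the present SAP was signed before the final lock of the open-label extensions. A reader might infer that Holm can simply replace 0.025 in SAP 4.4.1. It cannot: relaxing the second threshold after the primary analysis would be post hoc and would not carry the error control claimed for it.

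A reader might also infer that the fixed rule is a mistake. It is not. It controls the error as protocol 10.3.3 intends, the plan sets no target for both doses succeeding, and the chance of at least one success is the same under either rule. This is a gain in efficiency on what the protocol treats as a secondary analysis.

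The figures depend on the test. SAP 4.4.1 specifies stratum-adjusted logistic regression without saying which test statistic. Ignoring strata, a likelihood-ratio test gives 85.2% to 91.4%. A Wald test gives 42% to 58%, because it fails when 0.3 mg/kg has no responders (probability 0.95²⁴ = 0.29). Holm is ahead in each case.

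The shared bound does not mean equal use of it, as Step 4 shows. It also holds only as far as each test keeps its own level. In the Step 4 scenario the likelihood-ratio test gives 3.8% (fixed) and 7.3% (Holm), because that test is itself too liberal at low rates and this sample size.

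Finally, a reader might expect a large gain on the 10% claims. At the planned 24 per arm there is none; the rise from 83.1% to 92.1% needs both 28 treated and an assumed 39.1% rate. Holm would also make the interval used for one dose depend on the other dose's result.

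**Conclusion.** The point holds as a low-cost improvement, not as an error. For the two comparisons with 0.3 mg/kg, Holm keeps the nominal 0.05 familywise bound, never rejects less than the fixed rule, and adds 6.3 points to the chance that both doses succeed at the planning rates. The gain is about 4 to 11 points across the settings tabulated. These figures assume independent binomial arms, an unstratified test and the stated rates. The documents do not support calling the fixed rule invalid, calling the trial underpowered because of it, or changing the Stage 2 decision rule now.

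**What to change.** In protocol 10.3.3 and 10.6.1.3.1, state Holm's procedure at an overall two-sided 0.05: test the smaller of the two p-values (3 and 10 against 0.3 mg/kg) at 0.025 and, only if it is significant, the other at 0.05. This is a prospective rule; an amendment made once results are known would need the same post hoc label as the SAP.

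In SAP 4.4.1, keep the 0.025 decision as the pre-specified one. Report the Holm result beside it, labelled as added after the Stage 2 primary analysis, and name the logistic regression test to be used.

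For the 10%-threshold claims Holm is optional, and leaving the 97.5% rule alone is reasonable.

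The cost is a few sentences and no extra subjects. The price is the higher use of the 5% bound when only one dose is ineffective (1.7% to 3.7% in the Step 4 scenario).

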- Myeloblasts and cellularity will be presented at baseline, Weeks 12 and 24 as well as change from baseline
- Collagen grade shifts relative to baseline at Weeks 12 and 24.

The modified MPN-SAF TSS will be presented descriptively at baseline and at the beginning of each cycle (Cycle 2 onward). In addition, the number of subjects with \geq 25% and \geq 50% reduction relative to baseline at the beginning of each cycle (Cycle 2 onward) will be presented.

Stage 2:

Duration of effect of the three doses on reduction in bone marrow fibrosis:

- To assess the duration of effect of the three doses on bone marrow improvement a
 Kaplan-Meier plot will be provided. Duration of BM improvement will be defined for
 responding subjects as time from first decrease from baseline of one grade to time of
 return to baseline levels. If no return to baseline levels then duration will be
 censored at the last BM assessment
- Effect and duration of effect of the three doses on disease related anemia, thrombocytopenia, and constitutional symptoms: For patients with improvement, the duration of improvement is defined as the number of weeks of improvement from the first12 weeks of improvement period.

IWG-MRT response will be summarized by treatment group at each visit by percent of subjects with complete response, partial response, clinical improvement, stable disease and progressive disease according to IWG-MRT criteria.

4.4.3 Exploratory Efficacy Endpoints

The exploratory endpoints will be summarized using tables, listings and graphs as appropriate.

4.4.4 Sensitivity Analyses

For Stage 2, a non-stratified analysis of BMRR will be computing as a sensitivity analysis.

4.4.5 **Subgroup Analyses**

Stage 1:

• Primary endpoint results will be presented by risks groups (intermediate-1, intermediate-2, or high risk subjects).

Stage 2:

- Primary endpoint results will be presented:
 - by risks groups (intermediate-1, intermediate-2, or high risk subjects)
 - for each strata separately (baseline anemia alone, baseline thrombocytopenia alone, baseline anemia and thrombocytopenia)
 - by transfusion status at baseline with transfusion dependency defined as: ≥ 2
 units PRBC every 4 weeks for 12 weeks prior to or after C1D1
 - by PTX-2 level at baseline classify by High/Low category (median as the cutoff)

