4.9 MISSING DATA

All available efficacy and safety data will be included in data listings and tabulations. No imputation of values for missing data will be performed. Subjects with missing post baseline response data, for any reason, will be counted as non responders.

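### SAP 4.4.1 calls scoring missing biopsies as non-response conservative; that holds for the 10% threshold but is not guaranteed for the two superiority tests against 0.3 mg/kg, and SAP section 4 never varies the rule

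*SAP*

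**What the plan says.** SAP 4.4.1 (Stage 2) gives one rule for subjects without a usable marrow result: "For subjects with no readable post-baseline BM biopsy results available, the conservative rule to consider them as non-responders will be used". SAP 4.9 widens it: "Subjects with missing post baseline response data, for any reason, will be counted as non responders". The primary efficacy population in SAP 4.1.1 is everyone randomized and dosed, so each subject without a biopsy stays in the denominator as a failure.

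Section 4.4.1 uses this endpoint in two ways:

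- One-arm rule for 3 and 10 mg/kg: "the lower limit of the 97.5% two-sided confidence interval will be compared to this threshold of 10"%.
- Between-arm tests: "The BMRR will be analyzed using a logistic regression with bone marrow response at any time during the study (yes/no) as response variable", adjusted for stratum. The 3 versus 0.3 and 10 versus 0.3 mg/kg contrasts "will be computed with the aim to demonstrate superiority and therefore, will use an adjusted two-sided level of significance of 0.025".

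The only Stage 2 entry in SAP 4.4.4 is that "a non-stratified analysis of BMRR will be computing as a sensitivity analysis". The subgroup analyses in 4.4.5 use the same endpoint, and 4.2 tabulates reasons for discontinuation by arm without re-analysing response.

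The protocol planned more. Its Full Analysis Set (FAS, section 10.5.1) needs a post-baseline marrow assessment, except for subjects stopping for toxicity within the first cycle. Its Per Protocol (PP) set is a subset with at least three cycles of drug. Section 10.6.1.3.1 runs the pairwise comparisons on both. The SAP reprints the FAS and PP definitions in its Appendix 3 synopsis, but sections 4.1 and 4.4 define and use neither.

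**The concern.** Against a fixed 10%, counting missing as failure works against the drug. In a comparison of two doses it lowers both arms, and each failure imputed to the reference arm helps the higher dose. The label in 4.4.1 draws no such distinction.

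Stage 2 has no untreated control. Protocol 1.5 (control-arm row) says a dose response will count as evidence of efficacy, so the two contrasts with 0.3 mg/kg carry weight. The first post-baseline biopsy is at Cycle 4 Day 1, about Week 12 (Protocol 7.11.1), so a subject who leaves before then will normally have no outcome. If such losses were heavier at 0.3 mg/kg, a superiority claim could partly reflect who was biopsied, while the reader is told the rule guards against this.

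**Working it through.** **The plan's own figure.** Protocol 10.1 states 82% power for 24 per arm, a 39-point difference with the better rate at 46% (so 7% versus 46%), two-sided 0.025. The pooled normal approximation without continuity correction gives 0.8196, so the figure reproduces.

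**Inputs from the documents.** Each test is two-sided at 0.025, so 1.25% in the favourable direction. Protocol 10.1: "The trial will enroll 84 subjects to allow for a discontinuation rate of 15"%; at 1:1:1 that is 84/3 = 28 per arm. Planned response is 5% at 0.3 mg/kg and 46% at 10 mg/kg (at least 46% at 3 mg/kg).

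**Assumed.** The share without a readable biopsy is not given by arm. Call it m_c for 0.3 mg/kg and m_t for the higher dose, unrelated within arm to the unseen response.

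**Formula.** With true rates p_c and p_t, the scored rates are p_c(1 − m_c) and p_t(1 − m_t). The scored difference is therefore

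(p_t − p_c) + (p_c·m_c − p_t·m_t).

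The second bracket is the bias. Its sign depends on p_c·m_c against p_t·m_t, not on the loss alone.

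**One-arm threshold.** p(1 − m) never exceeds p, so the rule is conservative there.

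**Equal true rates** (the case that governs false positives). The bias is p(m_c − m_t), positive whenever m_c exceeds m_t. At m_t = 5% and m_c = 25%:

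| True rate | Scored, higher dose | Scored, 0.3 mg/kg | Spurious difference |
|---|---|---|---|
| 20% | 19.0% | 15.0% | 4.0 points |
| 30% | 28.5% | 22.5% | 6.0 points |
| 46% | 43.7% | 34.5% | 9.2 points |

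Probability of falsely declaring the higher dose superior, by exact enumeration of two binomials, 28 per arm, nominal 1.25%. The Wald test is an unstratified logistic regression with empty cells counted as no rejection. Loss is higher dose / 0.3 mg/kg.

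| Loss | Test | 20% | 30% | 46% |
|---|---|---|---|---|
| 15/15 | Wald logistic | 0.3% | 0.9% | 1.0% |
| 15/15 | pooled z | 1.3% | 1.2% | 1.1% |
| 10/20 | Wald logistic | 0.6% | 1.7% | 2.4% |
| 10/20 | pooled z | 2.1% | 2.3% | 2.7% |
| 5/25 | Wald logistic | 1.0% | 3.0% | 5.3% |
| 5/25 | pooled z | 3.2% | 4.0% | 5.7% |

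The Wald rows are closer to the SAP's model. At a 20% response rate they stay below 1.25% throughout. With both arms at 5% and 5/25 loss, even the pooled z-test gives only 0.34%.

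**Planned rates (5% versus 46%).** The bias is 0.05·m_c − 0.46·m_t, positive only if m_c > (0.46/0.05)·m_t = 9.2·m_t. At 5/25 the difference becomes 0.46 × 0.95 − 0.05 × 0.75 = 0.437 − 0.0375 = 39.95 points, against a true 41. At 5/15 it is 0.437 − 0.0425 = 39.45. Only a pattern such as 0/30 raises it: 0.46 − 0.035 = 42.5.

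On the odds-ratio scale, which the logistic model uses, break-even m_c is 8.5%, 16.4% and 23.7% for m_t of 5%, 10% and 15%, about 1.6 to 1.7 times m_t. At 5/25 the odds ratio rises from 16.2 to 19.9.

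**The case against.** A reader might infer that the rule favours the higher dose whenever more 0.3 mg/kg subjects are lost. The documents do not support that. At the plan's own rates the risk difference normally shrinks, and the odds ratio moves up only past the break-even above. Nor does inflation of several times nominal hold throughout: at a 20% response rate the Wald test stays under its nominal level.

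The scenarios can also be challenged. Expecting more loss at 0.3 mg/kg because it is nearly inactive sits badly with error rates computed as if it worked equally well. Subjects, investigators, assessors and sponsor are blinded (Protocol 6.5). Response counts at any of three biopsies, so a 25% unevaluable share in one arm exceeds the whole 15% discontinuation allowance. Toxicity could remove more subjects at the higher doses, and then the rule would be conservative. All this limits the likely size; it does not make the label correct for the tests.

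A reader might also infer that nothing planned anywhere addresses the point. That is true of SAP section 4 only: the protocol's FAS and PP comparisons drop most or all subjects without a biopsy. Moreover, SAP section 1 says the Stage 2 primary analysis followed an earlier SAP, which is not among the documents. What remains is that the current SAP, which governs the final analysis, does not carry those comparisons forward.

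Finally, treating early discontinuation as failure is a legitimate composite choice. That supports keeping it as the main analysis, not calling it conservative for every use.

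**Conclusion.** The point holds in a limited form. The label is justified for the 10% threshold and not guaranteed for 3 or 10 mg/kg against 0.3 mg/kg. With similar true response and heavier loss at 0.3 mg/kg, the rule pushes toward superiority of the higher dose. Under an assumed 5/25 loss and the Wald test, false superiority is about 2.4 times nominal at a 30% response rate (3.0/1.25) and 4.2 times at 46% (5.3/1.25), and is not above nominal at 20%.

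These figures rest on 28 treated per arm, no stratification, missingness unrelated to the unseen response within arm, and assumed loss rates; the documents do not show that loss will be unequal. The gap in SAP section 4 needs no such assumption: every Stage 2 analysis of the primary endpoint there uses the same scoring.

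**What to change.** Keep non-responder scoring for the main Stage 2 analysis, and change the SAP as follows:

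1. In 4.4.1, restrict the word conservative to the 10% threshold, and say that for the pairwise tests the direction of any bias depends on response and loss in both arms.
2. Tabulate subjects without a readable post-baseline biopsy by arm and reason, beside the discontinuation table in 4.2.
3. In 4.4.4, for the two superiority contrasts, restore the protocol's FAS and PP comparisons. State which definitions apply: Protocol 10.3.4 scores subjects with no central assessment as non-responders while 10.5.1 leaves most of them out of the FAS, and the synopsis and 10.5.1 define PP differently.
4. Add a tipping-point analysis. Set unevaluable 0.3 mg/kg subjects to responders one at a time, hold unevaluable higher-dose subjects as non-responders, and report the count at which significance at 0.025 is lost.

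Multiple imputation at the pooled stratum rate may be shown as support. It should not decide whether a result is called robust, since it pulls the arms together when a real effect exists and would be sparse with about 28 per arm over three strata.

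The cost is a wording change and some extra analysis of existing data. The downside is that a superiority result may have to be described as less robust.

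### The stated probability above 0.999 that a dose arm clears the 10% threshold is 0.971 on the protocol's own inputs, and between about 0.91 and 0.98 under the SAP's population and missing-biopsy rule.

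*SAP*

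**What the plan says.** Protocol 10.1 sizes Stage 2 on 24 subjects per arm: "The chosen sample size of 72 subjects (i.e. 24 subjects per dose arm"). It then adds an allowance: "The trial will enroll 84 subjects to allow for a discontinuation rate of 15"%. Allocation is equal (Protocol 10.2: "This study is randomized with a 1:1:1 randomization ratio"), so 84 enrolled means 28 per arm. The assumed response rates are 5% in the 0.3 mg/kg arm and "46% in the 10 mg/kg arm and at least 46% in the 3 mg/kg arm".

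On these figures 10.1 says that the probability of success when "comparing the lower limit of the exact 97.5% two-sided confidence interval of the observed rate to 10% is larger than 0.999". Protocol 10.6.1.1 applies the rule dose by dose.

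The SAP keeps the rule. In 4.4.1, for the 3 and 10 mg/kg groups, the "lower limit of the 97.5% two-sided confidence interval will be compared to this threshold of 10"%. What changes is who is analysed. SAP 4.1.1 makes all randomized and treated subjects the primary efficacy population, with no biopsy requirement. For subjects with no readable post-baseline biopsy, SAP 4.4.1 says "the conservative rule to consider them as non-responders will be used", and SAP 4.9 treats missing post-baseline response data in the same way. By contrast, the protocol's Full Analysis Set (10.5.1) requires a post-baseline assessment, except for early discontinuation due to toxicity. SAP 2.5 gives no new calculation. It refers to the appended protocol synopsis, which refers to the protocol body, so the 10.1 figure is carried forward unrevised.

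**The concern.** The probability in 10.1 is the operating characteristic of the primary efficacy claim, and two things about it look wrong. First, a value above 0.999 is high for an exact interval on 24 subjects, where the threshold falls on a whole number of responders. Second, 10.1 removes the expected losses from the denominator (84 enrolled, 72 analysed), whereas the SAP keeps every treated subject and counts those without a readable biopsy as failures. At stake is how a dose that misses the threshold is read. A reader relying on 10.1 would take a miss as practically impossible at a true rate of 46%.

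**Working it through.** **Inputs.** n = 24 per arm, rate 0.46, exact two-sided 97.5% interval (0.0125 in each tail), threshold 10%, 84 enrolled and 15% discontinuation (Protocol 10.1); 1:1:1 allocation (Protocol 10.2); all-treated population and non-responder rule (SAP 4.1.1, 4.4.1, 4.9); biopsies at weeks 12, 24 and 36 (Protocol 7.11.1).

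**Method.** The Clopper-Pearson lower limit for x responders of n is the 0.0125 quantile of Beta(x, n − x + 1). Let r be the smallest x whose lower limit exceeds 10%. The success probability is P(X ≥ r) for X ~ Binomial(n, p).

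**Step 1: the protocol's own figure.** With n = 24, 6 responders give a lower limit of 8.4% and 7 give 11.0%, so r = 7. P(X ≥ 7 | 24, 0.46) = 0.971. The stated value does not reproduce. Other per-arm calculations at n = 24:

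| Method | Probability |
|---|---|
| Wilson 97.5% (r = 6) | 0.990 |
| Wald 97.5% (r = 8) | 0.928 |
| Exact 95% (r = 7) | 0.971 |
| Exact 90% (r = 6) | 0.990 |
| Normal approximation, null and alternative variances | 0.986 |
| Normal approximation, null variance only | 0.9999 |

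Only the last exceeds 0.999, and it is not the exact interval that 10.1 names. A reading in which at least one of two independent arms succeeds gives 1 − (1 − 0.971)² = 0.9991.

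**Step 2: the SAP basis.** 84 / 3 = 28 treated per arm. With n = 28, 7 responders give a lower limit of 9.3% and 8 give 11.7%, so r = 8. If a share d of treated subjects has no readable post-baseline biopsy and 46% applies to the rest, the analysed rate is 0.46 × (1 − d):

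| d | Analysed rate | P(X ≥ 8 of 28) |
|---|---|---|
| 0% | 0.460 | 0.981 |
| 5% | 0.437 | 0.967 |
| 10% | 0.414 | 0.945 |
| 15% | 0.391 | 0.912 |

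**Step 3: splitting the gap.** From 0.999 to 0.971, about 0.03, is an error in 10.1 that is present before any dropout. From 0.971 to 0.912, about 0.06, is the most that the SAP rule adds at 15% discontinuation.

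**Step 4: the other figures in 10.1.** The 95% half-width is 1.96 × √(p(1 − p)/n).
- Higher-dose arms, stated ±20 points: 19.9 at n = 24 and p = 0.46; 18.1 at n = 28 and p = 0.391.
- 0.3 mg/kg arm, stated ±8 points: 8.7 at n = 24 and p = 0.05; at n = 28, 7.5 with p = 0.85 × 0.05 = 0.0425, and 8.1 with p = 0.05.
- Pairwise power, two-sided 0.025, pooled normal formula: 46% versus 7% at n = 24 gives 0.820, which reproduces the stated 82%. At the planning rates of 46% and 5%, n = 24 gives 0.875. With both rates multiplied by 0.85 (39.1% versus 4.25%), n = 28 gives 0.846, still above 82%.

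**The case against.** **The SAP does not fail every dropout.** A reader might infer that all 15% become non-responders, so that the true figure is simply 0.91. The documents do not support that. The rule covers only subjects with no readable post-baseline biopsy, response counts at any time during the study, and the first post-baseline biopsy is at week 12. A subject who leaves after that biopsy keeps any response already seen. The 0.912 is the worst case at the assumed 15%; if half of those discontinuing lack a biopsy (7.5%), the figure is 0.957. This objection stands.

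**The 46% may already include non-responders.** Protocol 10.1 calls it the response rate on the primary endpoint, and 10.3.4 already counts subjects without a central assessment as non-responders. If so, multiplying by 0.85 double-counts and 0.981 applies. The Full Analysis Set definition in 10.5.1 points the other way. The documents do not settle it, so the range is needed.

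**The figure may mean at least one of two arms.** That gives 0.9991 at n = 24, and 1 − (1 − 0.912)² = 0.992 in the worst case under the SAP. However, 10.1 does not say so, and both documents make the claim for each dose separately. This does not rescue the figure.

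**The interval method is open.** The protocol says exact in 10.1 and 10.3.3, but 10.6.1.1 asks for a method consistent with the stratified design, and the SAP names none. At 28 per arm and 39.1%, Wilson gives 0.961 and Wald 0.828. This limits the precision of the restated figure. It does not restore 0.999.

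**Timing.** SAP section 1 says that an earlier Stage 2 SAP was signed before the Stage 2 primary database lock, and that this one was prepared for the final analysis. No enrolment decision depends on the correction. That limits its consequence, not its accuracy.

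**Conclusion.** The concern holds for one figure. The probability above 0.999 is 0.971 per arm on the protocol's own inputs. Under the SAP's population and rule it lies between 0.912 and 0.981 per dose for 15% down to 0% without a biopsy. The chance that a dose with a true 46% rate misses the claim is thus about 2% to 9%, against a stated figure below 0.1%. No exact per-dose calculation reaches 0.999, so the need to correct does not depend on the dropout assumption. The size of the correction does: it assumes Clopper-Pearson limits, 28 treated per arm, and 46% as the rate among subjects with a biopsy.

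Two stronger readings should be avoided. One is that the SAP's handling of dropouts explains the whole fall from above 0.999 to 0.91; about 0.03 of it is there before any dropout. The other is that the sample-size section fails as a whole. Precision is about as stated or better on the SAP basis (the ±8 points for the lowest dose is itself 8.7 by the usual formula at 24), and pairwise power at the planning rates is about 85% against 82%. One qualification: the 82% is strictly computed for 46% versus 7%, and if that pair were diluted in the same way (39.1% versus 5.95%, n = 28), it would be 78.6%. The protocol draws its conclusion for 46% versus 5%, where the claim stands.

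**What to change.** In Protocol 10.1, replace the value above 0.999 with 0.971 per arm for 24 subjects (at least 7 responders). In the SAP, at 2.5 or 4.4.1, state that on the all-treated basis of about 28 per arm at least 8 responders are needed. Give the probability per dose as 0.981, 0.967, 0.945 and 0.912 for 0%, 5%, 10% and 15% of subjects without a readable post-baseline biopsy. State the assumptions alongside: 46% applies to subjects with a biopsy, and limits are Clopper-Pearson. Name the interval method in SAP 4.4.1 so that the figure and the analysis match. If the protocol text can no longer be amended, a note in the SAP or the clinical study report serves the same purpose. The cost is a few lines of text and a less favourable stated probability, with no extra subjects and no change to the design or the decision rule.
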